## **Computer-based intervention for battered sheltered women with substance use**

### **Overview**

Substance use and intimate partner violence victimization (IPV) are significant and interrelated public health problems facing women. For battered women, the presence of substance use increases the risk of re-victimization and the risk of more severe abuse. Moreover, given the multitude of competing concerns and the high degree of stress faced by battered women during and after their shelter stay, women with prior substance use problems are at high risk for substance use relapse. Further, substance use difficulties can compromise battered women's ability to access and effectively use integral community resources, interfering with their ability to establish long-term safety for themselves and their children.

Battered women's shelters provide emergency shelter to approximately 300,000 women and children each year. A prime time to intervene with battered women might be when they enter a shelter and have already initiated a change in their lives. Thus, a shelter-based intervention for battered women that addresses substance use problems might reduce the risk of substance use, reduce the risk of future IPV, and improve utilization of substance use treatment. Recent surveys of battered women programs have found that although program staff recognizes that substance use problems are common among their clients, these programs have limited substance use assessments and interventions in place and only a minority of staff has substance abuse training. Further, a huge challenge for these battered women shelters is the lack of financial resources to provide substance use services to their residents, especially with current decreases in their federal and local funding and increases in demand for their services. A computer-delivered intervention for battered sheltered women with substance use problems is a novel approach that can overcome existing obstacles to addressing substance use in battered women shelters, particularly time, training, and cost limitations.

The proposed study will develop and assess an innovative, easily implementable, low-cost, computer-delivered intervention, the SHE Program (Safe and Healthy Experiences) that will address known barriers in early identification and intervention for battered sheltered women with substance use issues. The computer-based SHE Program will be based on motivational interviewing a well-defined intervention strategy that has yielded particularly promising results in a range of clinical issues and a range of patient populations, including substance using women and women with IPV. Motivational interviewing with its non-confrontational and collaborative approach and its emphasis on increasing autonomy, self-efficacy, and skill sets is consistent with an empowerment model; a highly recommended intervention model for victimized women.

### **The pilot study aims are to:**

1. Develop our proposed preliminary computer-based intervention, incorporating information gained in focus groups.
2. Perform a small open trial (N = 15) of SHE to assess feasibility of recruitment of target population and acceptability of intervention and study procedures.
3. Conduct a randomized pilot trial in a sample of 60 battered sheltered women who report substance use problems within the three months prior to entering the shelter, to demonstrate the feasibility of SHE and the acceptability of SHE via participant report of ease of use, helpfulness, and overall satisfaction.
4. Examine preliminary evidence that relative to control condition, the computer-based intervention (SHE) will result in improvements in our primary outcomes of substance use (heavy drinking or drug using) days over a 6-month post-shelter period and in our secondary outcomes of greater use of substance use services (both treatment and self-help utilization) and reduced IPV severity over a 6-month post-shelter period. Theorized

mediators include readiness to change and self-efficacy for behaviors related to substance use.

## Background

Violence against women is a significant public health problem. Intimate partner victimization (IPV) is defined as violence by an intimate partner that may involve physical altercations (e.g., such as hitting, slapping or kicking), emotional or physical threats, and/or forced sexual relations. IPV is a widespread and significant public health problem. Approximately 5.3 million adult women in the U.S. experience victimization annually, which results in nearly 2 million injuries and 1,300 deaths; one of the leading causes of injuries to women. The degree of morbidity associated with IPV is reflected in the fact that it negatively affects eight of the ten leading health indicators identified by the Department of Health & Human Services (DHHS). Estimates of the medical cost burden of IPV range from USD 2.3 billion to USD 7.0 billion annually. Further, there is accumulating evidence to suggest a significant relationship between maternal IPV and maternal child abuse and maltreatment.

In recognition of the significant social problems posed by IPV, battered women shelters, which provide physical safety, as well as emotional support, are prevalent throughout the country. There are approximately 2,000 community-based shelter programs throughout the US, providing emergency shelter to approximately 300,000 women and children each year. Considering the number of women who seek help from these facilities and that sheltered battered women have already instituted a change in their life, a prime time to intervene may be while these women are already seeking help from shelters.

Substance use problems are highly prevalent in battered women: Lifetime prevalence rates for substance abuse or dependence are twice as high for women with IPV than women in the general population and battered women are 5.6 times more likely to develop a substance use disorder compared to women not exposed to IPV. For women in U.S. domestic violence shelters, it has been estimated that 42% are substance users. Moreover, given the multitude of competing concerns and high degree of stress faced by battered women in shelters and when they leave shelters, women with prior substance use problems appear to be at high risk for relapse. Common theories to explain the strong association between these two phenomena have included the self-medication hypothesis, that is, IPV victims use substances to cope with the effects of violence. Conversely, substance use can impair a woman's judgment or compromise her ability to move to safety (see review). A third possibility is that substance use may increase conflict in relationships, leading to violent behavior towards the woman, especially if her partner is also using alcohol or drugs. The pathways linking IPV and substance use are complex. In general research supports a strong bidirectional relationship between these two morbidities. A longitudinal study of a national probability sample of 3,006 women followed for 2 years identified a cyclic relationship where drug use increased the risk of IPV and IPV increased the risk of both drug and alcohol use.

Recent research has demonstrated that comorbid substance use increases risk of new episodes of violence for women with IPV: In their comprehensive model of variables associated with a battered woman's risk for future IPV, Foa et al. suggested that negative consequences of IPV such as substance use can, in turn, impede a women's ability to curtail future violence. Consistently, longitudinal studies have found that substance use is associated with new episodes of abuse in battered women. Furthermore, drug use is related to increased severity of physical partner victimization. Given that cessation of violence is necessary for recovery from its traumatic effects, it seems imperative to address victimized women's substance use difficulties. Such an intervention may improve battered women's ability to effectively use resources to help break the cycle of violence and establish their and their children's safety.

Why shelter stay is an opportune time to address substance use issues: There is consensus among experts that a critical time to provide substance use interventions for women with IPV is when they are seeking shelter services, because at these times women are open to changes in their lives and identities and most likely to recover from violence and from substance use. In general, the current literature supports interventions that target both IPV and substance use. The Substance Abuse and Mental Health Services Administration (SAMHSA) in the United States has identified service system integration as a key domain to improving services for women with substance use and violence in their lives and have highlighted the importance of the need to involve diverse organizations, such as domestic violence programs in these integration efforts.

Despite the need, few battered women shelters address substance use issues among their residents. Unfortunately, few battered women shelters address substance use issues, even though substance use is extremely prevalent in this population. A survey of battered women shelters, found that although the program staff recognize that substance abuse problems are common among their clients, these programs have limited substance use assessments and interventions in place, and only a minority of staff have training in substance use issues. Furthermore, a huge challenge for these battered women shelters is the lack of financial resources to provide these substance use services to their residents, especially with current decreases in their federal and local funding and increases in demand for their services.

Our proposed project, will develop and assess an innovative, high-reach, easily implementable, low-cost computer-delivered intervention (Safe and Healthy Experiences; The SHE Program) that will address known barriers in early identification and intervention with sheltered battered women with substance use problems. Given the number of battered women shelters in the country, our proposed intervention, SHE, has the potential to impact a relatively large community of women and children and to significantly reduce the suffering associated with IPV and substance use. A computer-delivered intervention, if proven effective, can be widely disseminated while maintaining treatment fidelity across sites and may hold promise for other IPV populations with substance use issues.

The overall goal of the SHE Program will be to facilitate self change as well as treatment and community resource engagement with respect to substance use issues. The content of SHE will be theory-driven, consistent with a motivational interviewing (MI) model of behavior, and consistent with the literature on effective interventions for our target population and targeted risk factors. MI is a well-defined intervention approach, has been used to reduce drug use among non-treatment seekers, has wide dissemination, and demonstrated efficacy across a range of behavioral areas including substance use and across a range of populations including high-risk women. Consistent with the Transtheoretical Model (TTM), MI utilizes stages and processes of change, evolving readiness and self-efficacy to change. Ambivalence about change is considered normative within the motivational interviewing framework. The client's readiness to make changes is not assumed. Instead, an important exercise in MI is the exploration of level of readiness to change. The intervention is appropriate for varying levels of readiness to change. MI facilitates internal motivation to change through alignment of behavior change with deeply held beliefs, values, and goals.

The MI model is of particular value for substance using women with IPV in reducing their risks because MI has a non-confrontational and collaborative approach, emphasizes increasing a participant's awareness to successful steps towards their own well-being, identifies participant's strengths, and builds upon participant's successes. Such an approach is consistent with recommendations for brief interventions in substance users and for women with IPV. In fact, recently, the World Health Organization has recommended a MI-consistent approach for intervening with women who have experienced IPV. Further, a MI approach is in keeping with the empowerment model, a highly recommended intervention model for women with interpersonal violence. The MI and IPV Workgroup (2010) have suggested

that the empowerment model and MI models converge around important principles, such as increasing autonomy, self-efficacy, and skill sets.

## **Summary**

Our proposed project will develop and assess an innovative, easily implementable, low-cost computer-delivered intervention, the SHE Program, that will address known barriers in early identification and intervention with sheltered battered women with substance use issues. Considering the number of women who seek help from battered women shelters and that sheltered battered women have already instituted a change in their life, battered women shelters is a prime setting for a substance use intervention. Further our proposed brief computer-delivered intervention is well suited to battered women shelters because it addresses the limited time, resources, and training of shelter staff in providing substance use interventions. Finally, a computer-delivered intervention, if proven effective, can be widely disseminated while maintaining treatment fidelity across battered women shelters and may hold promise for other battered women with substance use issues in other settings.

## **Methods - General**

### **Subjects and Recruitment Site**

Participants for the RCT and Open Trial will be recruited from the Women's Center of Rhode Island (WCRI), Sojourner House, New Hope, and Battered Women's Shelter of Summit and Medina Counties. Participants eligible for the screening portion of the study will be residents at the women battered shelter, the Women's Center of Rhode Island (WCRI), Sojourner House, New Hope, or Battered Women's Shelter of Summit and Medina Counties. Shelter staff will inform research staff as new residents are admitted to the shelter. The research assistant (RA) will attend house meetings and schedule times to be at the shelters when new residents are available and will provide a description of the initial study phase, the screening phase (Phase A). Research assistants will also give shelter staff business cards to refer clients to the study. Shelter residents will be recruited to participate in a computer-based survey to help battered women be healthy. Women who express interest will be given an information sheet (used to protect anonymity of those who did not qualify or chose not to participate in the full study). The information sheet will indicate that the purpose of screening is to find women who may be eligible for a study on risk factors for battered women and will describe what is involved with participating in the study. Women who verbally agree to participate will be given the opportunity to provide written consent to contact to set up a future appointment with the research staff. Women who refuse to complete screening for the study, or if after completing screening refuse to participate in the study, will be asked by the research assistant about possible reasons for refusal. Women who are interested will be screened for eligibility using the CIAS software delivered on an easy to use, ultraportable Tablet PC in a 10-15-minute screener (there will be no identifiers at screening) or a computer in a private setting. The use of Audio Computer-based Assisted Self-Interview (ACASI) software to conduct screening will maximize identification rates of women at risk for substance use. The screener will include a brief series of questions about general health, exercise, and diet. The screener will also include basic demographic questions as well as the following well-validated and reliable measures for this population: The NIDA-Modified Alcohol, Smoking, Substance Involvement Screening Test (NIDA-Modified ASSIST) will be used to assess for alcohol use, illegal drug use, and nonmedical prescription drug use in the past three months prior to shelter stay. Those who will be fully eligible for the study (and considered as at risk) will be categorized as an at-risk drinker and/or at moderate or high risk for substance use based on the NIDA-Modified ASSIST criteria for these risk categories. Women who have a prescribed medical marijuana card will be excluded from the study. The screener will also include a well-validated, reliable and recommended IPV measure. At screening, IPV in the past three months prior to shelter stay will

be assessed with the Woman Abuse Screening Tool (WAST). The WAST is an 8-item instrument that measures physical, sexual, and emotional abuse and is consistent with the definition of IPV as defined by The American College of Obstetricians and Gynecologists. It has correctly classified 100% of nonabused women and 92% of abused women in a known-group analysis, has good internal reliability, and has adequate concurrent validity, even with ethnic minorities. Consistent with similar studies, IPV status will be positive if a woman obtains a score of 4 or more on the WAST.

All participants screened will receive a standard health information brochure with further information and resources on the health topics mentioned, including a list of local substance use treatment referrals and community resources. Those meeting full inclusion criteria will be asked to provide signed informed consent and complete the computer based baseline assessments. All participants will be advised to keep their copy of the consent form in a secure location, or to discard this form if it is unsafe for them to keep it.

**Inclusion criteria:** Women who are 18 or older, residents of a battered women’s shelter (the Women’s Center of Rhode Island [WCRI], Sojourner House, New Hope, or Battered Women’s Shelter of Summit and Medina Counties), who are at risk substance users within the 3 months prior to entering the shelter, as determined by the screener, the NIDA-Modified ASSIST, and endorse IPV within the 3 months prior to entering the shelter, as determined by the screener, the WAST

**Exclusion criteria:** includes: 1) inability to provide informed consent (e.g., due to florid psychosis or other, clear cognitive impairment), 2) inability to understand English (understand the consent form when read aloud. 3) No endorsement on the baseline TLFB for substance use and/or intimate partner violence in the 3 months prior to shelter stay.

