*Recruitment and informed consent:* Shelter staff will inform research staff as new residents are admitted to the shelter. The RA will attend house meetings and schedule times to be at the shelters when new residents are available and will provide a description of the initial study phase, the screening phase (phase A). Shelter residents will be recruited to participate in a computer-based survey to help battered women be healthy. Women who are interested in participating in the screener will receive an information sheet, which will be summarized (and read for those who prefer this) in a private setting. The information sheet (used to protect anonymity of those who did not qualify or chose not to participate in the full study) will indicate that the purpose of screening is to find women who may be eligible for a study on health risk factors and will describe what is involved with participating in the study. Those women who verbally agree to participate will complete the 10-minute screener (there will be no identifiers at screening) using the CIAS software delivered on an easy to use, ultraportable Tablet PC. Women meeting study screening criterion (i.e., endorse substance use in the three months prior to shelter stay) will be given the opportunity to provide informed consent for the clinical trial, in a private setting. Research staff will carefully explain all aspects of the study to a potential recruit, including the risks and benefits and obtain participants' written informed consent. Recruits will be informed of the intervention commitment, amount and general types of assessments, and the follow-up procedures. The research assistant will orally describe the material written in the informed consent document and answer any questions the participant may have. Participants will be reminded that they are not required to participate in the study and that they will receive the standard care provided by the Women's Center, Sojourner House, New Hope, or Battered Women's Shelter of Summit and Medina Counties regardless of whether or not they choose to participate. Participants who give their consent will sign a copy of the document and will be given a signed copy of the informed consent document. Women who refuse to participate in the clinical trial will be provided referral information.

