Details of the research are not provided to anyone other than the actual participant. During each contact, participants will first be asked if it is a safe time to speak. Safe contact for follow-up assessments will be negotiated at each stage of the research. Both written and verbal contacts will be vague and never mention that the research involves partner violence. Follow-up interviews will be scheduled at a safe location. Safety plans will be negotiated up front (e.g., code words, cover story for reason for interview) if ever the abuser were to interrupt a phone call or assessment. Any handouts with important information (e.g., hotline numbers) will be available in wallet size copies without any reference to the study or name of organization. Participants' safety contact information will be updated monthly to determine if the contact information they previously provided is still accurate and safe. Participants will be given contact information for the research team and asked to let us know if the contact information they provided is no longer safe. All research personnel (i.e., interventionist, research assistant) will be able to call the PI for advice on any case where there is a concern for the safety of the respondent and the PI will be available at all times by pager.

Although the proposed intervention seeks to help a woman to develop strategies for keeping herself safe, it is possible that a woman who participates in the study might be at increased risk of partner violence because of increased assertiveness. At each follow-up assessment, our assessment of community resource use will ask about participants' visits to emergency rooms, health professionals, etc. The Composite Abuse Scale (CAS) will be administered to monitor abusive experiences in the context of a woman's relationship since the last assessment. Women will be asked at follow up assessments (3- and 6-month) about any occurrences of hospitalizations for medical, psychiatric, or substance use issues or emergency room visits, and whether or not any of these events were related to IPV in order to better gather information regarding any potential serious adverse events. These events will be reported to the Data Safety Monitoring Board (DSMB).

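### The protocol gives the screening information sheet two different stated purposes, one of which names battered women, and does not say whether women keep the sheet

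*Protocol*

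**What the plan says.** Subjects and Recruitment Site, under Methods - General, sets out the screening phase: "Women who express interest will be given an information sheet". The sheet is to state that screening aims to "find women who may be eligible for a study on risk factors for battered women".

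The recruitment and informed consent paragraph under Adequacy of protection against risks covers the same step: "Women who are interested in participating in the screener will receive an information sheet". Here the stated aim is to "find women who may be eligible for a study on health risk factors". Both places give the sheet the same function, which is to preserve the anonymity of women who turn out ineligible or decline the trial.

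Potential risks and Protection against risk both name the hazard: a participant still in contact with her abuser may face more abuse if the abuser learns that she is in the study. The response under Protection against risk includes this rule: "Both written and verbal contacts will be vague and never mention that the research involves partner violence". It also says that handouts with important information, such as hotline numbers, "will be available in wallet size copies without any reference to the study or name of organization".

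On study paper that a woman holds, Subjects and Recruitment Site says: "All participants will be advised to keep their copy of the consent form in a secure location, or to discard this form". No similar advice is given for the screening sheet.

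**The concern.** Two descriptions of one document cannot both be followed, and neither is marked as superseding the other. Staff at the four recruiting shelters could work from either.

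The difference matters because of a risk that the protocol itself identifies. A sheet that announces a study about battered women could tell a partner who finds it what the research is about. A sheet about health risk factors would not do so by its purpose line. The protocol accepts that study paper can be unsafe to hold, but attaches its advice only to the consent form. Consent is sought from women who meet the full criteria, so a woman who is screened and found ineligible receives the sheet but neither the form nor the advice.

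What is at stake is participant safety and consistency between sections. Endpoints, randomisation, sample size and analysis are not touched.

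**Working it through.** The check is mainly a comparison of text. The SAP says nothing on this point, so everything comes from the protocol.

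**1. Is it the same sheet?** Yes. Both sections place it before the screener, give it to women who show interest, and state the same anonymity purpose in nearly the same terms.

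**2. Do the stated purposes conflict?** Yes. "find women who may be eligible for a study on risk factors for battered women" names battered women; "find women who may be eligible for a study on health risk factors" does not. This conflict is explicit and needs no inference.

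**3. Which version fits the rest of the protocol?** The neutral one. The screener asks about general health, exercise and diet alongside substance use and abuse, and every screened woman gets a general health brochure. The safeguards under Protection against risk lean the same way: a phone line on which partner violence is not mentioned, vague contacts, and resource handouts stripped of study identity.

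**4. Do women keep the sheet?** This is not stated. One section says it is given, the other that it is received and then summarised or read in private. Neither says it is taken back. Retention is therefore a reasonable inference from silence, not a documented fact.

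**5. Does any advice cover it?** The secure-or-discard sentence names the consent form only. The optional one-page Safety Plan print-out, described under Study Procedure, carries no such advice either.

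**6. How many women?** The documents give no count. An illustration can use the 42% substance-use estimate cited under Background and Feasibility, assuming that this share of screened women qualifies and that all who qualify consent:

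- screened = enrolled / qualifying share = 60 / 0.42 = 142.9, about 143
- screened but not enrolled = 143 − 60 = 83
- with the 15 open-trial women, recruited from the same shelters: (60 + 15) / 0.42 = 178.6, about 179 screened, of whom 179 − 75 = 104 would not enrol

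These are not lower bounds. The 42% is an outside estimate for shelter residents in general. Women who volunteer for a health survey could have a higher rate, which would lower the counts. Refusals, the abuse criterion and the risk-level criterion would raise them. The counts measure women screened, not sheets kept or harm done.

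**The case against.** The strongest reply is that harm depends on three steps, none of which is documented: the wording is printed, the sheet is kept, and it is then found. The sheet itself is not in the material reviewed, from which consent pages were removed, and both sections only paraphrase it. The printed version may already be neutral. All of this stands, and it is why the point is conditional.

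The reply is also fair about the contact rule. "Both written and verbal contacts will be vague and never mention that the research involves partner violence" sits among provisions on safe times to call, follow-up arrangements and interrupted interviews. The handout rule concerns resource material. Both reach an in-shelter sheet by intent more than by letter. The protocol also does not ban all paper about abuse: at follow-up, women reporting current partner violence are given information on it.

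A reader might infer that the trial's safeguard fails at first contact, and that at least 83 women who never enrol leave holding a paper that identifies partner-violence research and are not contacted again. The documents do not support that. Printing and retention are unknown, and 83 is an illustration. The named risk is worded for participants, so extending it to women who are ineligible or decline is plausible but not stated. Nor is there a statement that such women have no further contact: those who refuse are asked why, and those who refuse the trial receive referral information.

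A last reply is that a vaguer purpose line discloses less. That is a real trade-off, but a limited one. Protection against risk already requires the sheet to warn clearly of possible distress from sensitive items, and this can stay beside a neutral purpose line.

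None of this removes the direct conflict between the two purpose statements or the gap in the secure-or-discard advice.

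**Conclusion.** The point holds as a conflict between two descriptions of the same sheet, together with an omission about what happens to it after screening. The conflict and the limited scope of the discard advice are explicit in the text. The safety consequence is conditional: it arises if the wording that names battered women is the one printed and if women keep the sheet.

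Its size cannot be established from the documents. The figure of about 143 women screened to enrol 60 holds only if 42% of those screened qualify and all of them consent. The conclusion does not depend on that count.

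The point is worth acting on because the hazard is one the protocol names, the replacement wording is already in the protocol, and the change is nearly free.

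**What to change.** - In Subjects and Recruitment Site, replace the purpose line with the neutral one already given under Adequacy of protection against risks, and check the printed sheet against it. Keep the notice of possible distress from sensitive items that Protection against risk requires.
- While checking, make sure the sheet does not carry the recruitment description of the survey, which also refers to battered women. The protocol uses that description in both sections but does not say it appears on the sheet.
- Either extend the secure-or-discard advice to the information sheet and other take-away print-outs, such as the Safety Plan, and give it to every woman who receives one, or state that the sheet is collected after it has been read.

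The cost is a slightly less explicit purpose line, a sentence or two of added text, and an IRB-approved reprint. Nothing changes in data collection, sample size or analysis.
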